7.2 Demographic and Other Baseline Characteristics

7.2.1 Demographic variables

Major demographic information is as follows:

1. Birth date
2. Gender (according to the protocol, only female could be enrolled)
3. Race

7.2.2 Medical history

The following information will be collected for the medical history of the subjects:

7.2.2.1 Angina pectoris

1. Basic information: classification (stable or unstable); duration (total years suffering from angina); frequency of angina attacks in recent one month (how many times/week); previous treatment procedures (PCI or CABG), time of the procedure; result of CTA or coronary angiography in recent 3 months (totally normal coronary/ coronary with occlusion <20%; which coronary branch, LM/LAD/LCX/RCA; the ratio of occlusion); history of MI or not, if yes, the time need to be recorded; result of ECG during exercise stress test or when angina attacks in recent three months; or results by myocardial nuclein perfusion imaging in recent three months;
2. Current medicine treatment at screening period of the study: name, dose, initiation date, frequency (month/year)
3. Emergency treatment: frequency and dose consumption of emergency medicine in recent one month (nitroglycerin or compound Danshen drip pill)

7.2.2.2 Other medical history

1. History of hypertension/ heart failure/ diabetes; the severity of these diseases; the current medicine therapy at the screening period of the study;
2. Other medical histories and concomitant medicines.

7.2.3 Vital signs and physical examination

Vital signs and physical examination should at least include the following items:

1. General status:

Heart rate (resting heart rate) measurement: sit rest for 5 minutes, no smoking, no excitatory food and beverage such as tea and coffee for 30 minutes, measurements are taken at sitting position for a continuous record of 3 minutes. Heartbeats in each minute are calculated and averaged to obtain the resting heart rate.

Blood pressure measurement: sit rest for 5 minutes, no smoking, no excitatory food and beverage such as tea and coffee for 30 minutes, measurements are taken at sitting position, with the elbow at the same level with the heart. Diastolic blood pressure is recorded at the fifth Korotkoff sound, repeated after 2 minutes and averaged. If the difference in diastolic blood pressure readings is $> 5\text{mmHg}$, measurement is repeated again after 2 minutes, and the 3 readings are averaged.

2. Physical examination of the respiratory system

3. Physical examination of the cardiovascular system

4. Physical examination of other systems

5. Body mass index: body weight (Kg)/Height ²(m²)

6. Measurement of waist circumference: At screening visit, under fasting, standing, calm breathing conditions, feet apart 25-30cm, waist circumference is measured at horizontal position at the midpoint of iliac spine and the 12th rib, with measuring tape close to but not press the skin, accurate to 0.1cm.

7.2.4 Lab test items

Lab examination should include at least the following items: hematological examination, echocardiography, rest and stress PET need to be done at the screening visit and last visit; ECG need to be done at every visit.

1. Hematology tests (all these lab test need to be done by fast in the morning):

a) Full blood count: red blood cell count, neutrophils, hemoglobin, white blood cell count and platelet count

b) Liver function (ALT, AST)

c) Kidney function (BUN, Cr)

d) Fasting blood glucose

e) Blood lipid levels (TC, TG, HDL-C, LDL-C)

f) Myocardial enzymes (CKMB)

g) Electrolyte (K, Na)

2. Routine urine test (PH, Specific gravity, Protein, Glucose, Ketone, Nitrite, Leukocytes, Hemoglobin, Red blood cells, Bilirubin), urine pregnancy test

3. ECG: heart rate; sinus rhythm/arrhythmia, depict what kind of arrhythmia; cardiac hypertrophy (yes/no); abnormal ST-T change (yes/no);

4. Echocardiography: to measure ejection fraction (EF%), left ventricular end systolic diameter (LVESD), interventricular septum thickness (IVST), left ventricular posterior wall thickness (PWT) and E/A ratio

5. Rest and stress PET: MBF of both rest and stress PET, then $MFR = MBF \text{ at stress} / MBF \text{ at rest}$ (the detailed description of PET test will be described in 7.3.1)

7.3 Assessment of Efficacy

7.3.1 MFR by PET

1. Radiation tracer: ^{13}N -ammonia; Hyperemic agent: Adenosine (ATP);

2. Patients were instructed to strictly refrain from any caffeinated substances for 24h before testing; All subjects fasted for >6 h;

3. PET: ^{13}N -ammonia PET was assessed in a 1-day protocol at rest and during Adenosine stress at a standard rate (0.12mg/min/kg) over 6 min. At rest, approximately 370~740 MBq of ^{13}N -ammonia was injected into a peripheral vein of all subjects, followed by a 30 mL saline flush. Dynamic and gated acquisition was initiated just before injection, and was extended for 20 min. Adenosine stress test was performed more than 50 min (5 half-lives) after rest protocol. During this time, ^{13}N activity at rest had physically decayed to about 3 % of its initial activity. ^{13}N ammonia and adenosine were infused through the peripheral veins of both the right and left arms (2-route method) to prevent suspending adenosine infusion during administration of ^{13}N -ammonia. ^{13}N -ammonia of the same dose (370~740 MBq) was injected at the end of the 3 min of administration. Images were acquired in 3-dimensional list mode on a Siemens Biograph64 TrueV PET scanner (Siemens Medical Solution, USA, Inc.), with a field of view 21.6 cm. The optimal imaging position was determined on a CT scout scan. Dynamic acquisitions of the emission scans were performed using a standard protocol using list mode for 20 min. Low-dose CT images were used for attenuation correction. Images were reconstructed using ordered subset expectation maximization (OSEM) method, and for review the images were resliced in short-axis as well as in vertical and horizontal long-axis orientation;

4. Data analysis. Regional ^{13}N -ammonia uptake was assessed using the 17-segment model and the semi quantitative scoring system of defect severity and extent, as recommended by the American Society of Nuclear Cardiology. A scan was considered normal if the summed stress score (SSS) was <4 , mildly abnormal if the SSS was between 4 and 8, and moderately to severely abnormal if the SSS was >8 , as previously reported in PET studies. Image interpretation according to these definitions was performed by 2 experienced readers. Diverging interpretations were resolved by consensus reading. Quantitative MBF

was determined using the PPD package developed and validated by PPD. A spherical region of interest was placed into the blood pool of the left ventricle. Myocardial and blood pool time-activity curves were generated from the dynamic frames and corrected for radioisotope decay. MBF was estimated by model fitting of the blood pool and myocardial time activity curves correcting for partial volume and spillover. MFR was calculated as the ratio of hyperemic to resting MBF.

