5.3 Selection of Trial Population

5.3.1 Inclusion Criteria

For inclusion in the trial, all of the following inclusion criteria must be fulfilled:

1. Female
2. Patients aged 18-70 years
3. Patients with typical stable angina but without coronary obstruction (defined as coronary occlusion <50%) by invasive coronary angiography or coronary computed tomography angiography (CTA) in recent three months
5. All other long acting cardiovascular disease medicines, including but not limited to aspirin/clopidogrel, CCB, ACEI/ARB, β -blockers, statins, ivabradine, trimetazidine, et al, should be stable taken for at least two weeks before screening period
6. For patients who met these five criteria above, MFR will be tested by stress PET. Patients whose MFR <3.0 could be included in the study

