6.10 Method of Blinding

NA

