8.1 Sample Size

This is an open-label, single arm trial intended to evaluate the improvement of microvascular function (myocardial blood flow reserve, MFR) by positron emission tomography (PET) after twelve week treatment with oral nicorandil in female non-obstructive CAD patients. The null hypothesis is that there is no difference between MFR at baseline and MFR after twelve weeks treatment. The alternative hypothesis is that the MFR after twelve weeks treatment is higher than the MFR at baseline.

Suppose the difference of MFR follows normal distribution, and the following assumptions are made to determine the sample size:

The mean value of difference of MFR is 0.55.

The standard deviation of difference of MFR is 0.56.

Alpha=0.05(two sided).

Power=0.80.

A sample size of 11 patients will be required to reach this goal. Assuming a drop-out rate of 30%, then a total of 15 patients will be recruited into this study. According to the recruitment progress, if there have been 11 patients complete their following period, this study could be accomplished when meet the end of the anticipated period of the whole study.

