8.3 Endpoints

8.3.1 Primary Endpoint

The primary endpoint is the difference of MFR by stress PET between baseline and after twelve-week treatment.

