10.2 Source Data and Subject Files

The Investigator must keep a subject file (medical file, original medical records) on paper or electronically for every subject included in the trial. This file will contain the available demographic and medical information for the subject, and should be as complete as possible. In particular, the following data should be available in this file: (adapt to trial as necessary)

Subject's full name,

Date of birth,

Sex,

Height,

Weight,

Medical history and concomitant diseases,

Prior and concomitant therapies (including changes during the trial),

Trial identification EMR200505-506

Date of subject's inclusion into the trial (i.e. date of giving informed consent),

Subject number in the trial,

Dates of the subject's visits to the site,
Any medical examinations and clinical findings predefined in the clinical trial protocol,
All adverse events observed in the subject,
Date of subject's end of trial, and
Date of and reason for early withdrawal of the subject from the trial or from the IMP, if applicable.

It must be possible to identify each subject by using this subject file.

Additionally, any other documents containing source data must be filed. This includes original printouts of data recorded or generated by automated instruments, photographic negatives, PET scan images, ECG recordings, laboratory value listings, etc. Such documents must bear at least the subject number and the date when the procedure was performed. Information should be printed by the instrument used to perform the assessment or measurement, if possible. Information that cannot be printed by an automated instrument will be entered manually. Medical evaluation of such records should be documented as necessary and the documentation signed and dated by the Investigator.

Certain data may be recorded directly in the CRF (or in a questionnaire, diary etc.) rather than entered into the subject's original medical file. In such cases there will be no record in the original subject file (either on paper or electronically) that corresponds to the entries in the CRF. In such cases, the data entered in the CRF will be considered source data. The clinical trial protocol should clearly and completely specify all those subject data in the CRF that will be considered source data. Data in the CRF that are not explicitly defined as source data will be entered in the subject's medical file.

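### PET quantification of the primary endpoint is not masked to visit, and the screening value that decides entry also serves as the baseline

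*Protocol*

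**What the plan says.** - **Design (8.1):** "This is an open-label, single arm trial intended to evaluate the improvement of microvascular function".
- **Primary endpoint (8.3.1):** "The primary endpoint is the difference of MFR by stress PET between baseline and after twelve-week treatment". Section 8.5.3 tests it with a paired t test.
- **Entry (5.3.1):** "Patients whose MFR <3.0 could be included in the study". Section 5.1.1 puts this PET inside the two-week screening period, so the value must exist before enrolment.
- **Baseline (8.5.2 and Appendix I):** baseline is the last value before the first dose, and only one PET is scheduled before treatment. The eligibility value and the primary baseline are therefore the same number.
- **Quantification (7.3.1):** "A spherical region of interest was placed into the blood pool of the left ventricle". Blood-pool and myocardial time-activity curves then go into a model fit that yields MBF, and "MFR was calculated as the ratio of hyperemic to resting MBF". Whether placement is manual or automatic, who does it, and what that person knows are not stated. The name of the software package is blacked out.
- **Readers (7.3.1):** "Image interpretation according to these definitions was performed by 2 experienced readers". The definitions meant are the summed-stress-score categories. The sentence does not cover MBF or MFR.
- **Blinding:** under "6.10 Method of Blinding" the only entry is NA. No section mentions masking of scans to visit, patient or order.
- **Retention (10.2):** source data to be filed are described thus: "This includes original printouts of data recorded or generated by automated instruments, photographic negatives, PET scan images".

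**The concern.** Treatment cannot be masked in a single-arm trial, but the visit at which a scan was taken can be, at the moment of quantification. The plan does not use this option.

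The order of events makes the omission matter. The screening scan is quantified when the result decides whether the patient can enter. The week-12 scan is quantified after treatment, and nothing in the plan hides that. A wish to enrol would favour a lower first value, and an expectation of benefit would favour a higher second one. Both would widen the difference in the direction of the alternative hypothesis. In a randomised comparison much of this would fall on both arms and cancel. Here it would be read as improvement on nicorandil.

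The two-reader consensus does not help, because it is attached to the visual score, which is not an endpoint. The primary measurement has no stated reader safeguard.

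**Working it through.** **Inputs.** From section 8.1: mean difference 0.55, SD of the difference 0.56, two-sided alpha 0.05, power 0.80, 11 evaluable patients, 15 recruited. From the synopsis and section 5.1.1: enrolment of 11–20. Assumed, because the protocol gives no reader-variability figure: a systematic shift b in the measured change of 0.10 or 0.20 MFR units, that is 0.10/0.55 = 18% or 0.20/0.55 = 36% of the planned effect.

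**Step 1: reproduce the plan's own figure.** For a paired t test, df = n − 1 and the noncentrality is δ√n/SD. At n = 11 this is 0.55 × √11 / 0.56 = 3.26. Exact power from the noncentral t distribution is 78.9% at n = 10 and 83.5% at n = 11. So 11 is the smallest n that reaches 80%, and the stated figure reproduces. Masking does not change it.

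**Step 2: the smallest mean change that reaches significance.** This is t(0.975, n − 1) × 0.56/√n:

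- n = 11: 2.228 × 0.56/3.317 = 0.376
- n = 15: 2.145 × 0.56/3.873 = 0.310
- n = 20: 2.093 × 0.56/4.472 = 0.262

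A shift of 0.10 to 0.20 is not small against these thresholds.

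**Step 3: rejection probability with no true change.** The measured difference then has mean b and SD 0.56, and the noncentrality is b√n/0.56. For example, b = 0.10 and n = 11 give 0.10 × 3.317/0.56 = 0.59.

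| Assumed shift b | n = 11 | n = 15 | n = 20 |
|---|---|---|---|
| 0 | 5.0% | 5.0% | 5.0% |
| 0.10 | 8.4% | 9.9% | 11.8% |
| 0.20 | 18.9% | 25.2% | 32.9% |

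These are two-sided probabilities of p<0.05. Almost all of the excess is in the direction of apparent benefit: at n = 11 the chance of a significant increase goes from 2.5% (b = 0) to 7.8% (b = 0.10) and 18.8% (b = 0.20). A larger sample makes matters worse, since a fixed bias is detected more reliably.

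**Step 4: is a masked quantification possible?** Section 7.3.1 acquires the data in list mode and section 10.2 keeps PET images as source data. Both scans of a patient exist once week 12 is done, so they can be processed together without labels. The screening quantification itself cannot be delayed, because entry depends on it. A second quantification of the baseline scan is therefore needed for the endpoint.

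**The case against.** The strongest reply is that the protocol is silent rather than wrong. A reader might infer that the region is placed by hand, that whoever quantifies the scans knows the visit, and that NA in section 6.10 rules out masked reading. The documents support none of these. The region is described in the passive, and the blacked-out software name leaves the degree of automation open. No section says what the analyst knows. Section 6.10 stands in the chapter on the investigational product, next to emergency unblinding, and most naturally concerns treatment blinding, for which NA is correct in a single arm. Nor should the two experienced readers be cited as the source of bias in MFR.

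The mechanism is also narrower than it may look. MFR is a ratio, so a placement habit common to the rest and stress scans of one visit tends to cancel. The incentive to read low bites only near MFR 3.0. The shifts of 0.10 and 0.20 have no source in the protocol. In so small a trial, staff who quantified a scan at screening may recognise it later. The trial is also a pilot meant to inform later studies.

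All of this stands, and it limits the claim. It does not remove it. Section 7.3.1 fixes tracer, dose, timing, scanner, reconstruction and model, and is the place where masking would be stated. Masking is a matter of measurement conduct and is not normally left to the SAP. A manual of operations appears in the abbreviation list, but the protocol does not refer this matter to it. A pilot whose results will feed a later design has its own reason to want an unbiased change in MFR.

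**Conclusion.** The point holds as an avoidable weakness in how the primary endpoint is measured. The plan has no masking to visit, a screening value that both decides entry and serves as baseline, and no control arm. Any reader-expectation bias would enter the paired difference in full.

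That such a bias will occur, or how large it would be, cannot be shown from the documents. The 8–12% and 19–33% figures are conditional on an assumed uniform shift of 0.10 or 0.20, the planned SD of 0.56 and no true effect. They show how sensitive the test is and do not estimate the bias.

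It would also be too strong to say that masking makes the before–after comparison unbiased. It acts on reader expectation only. Regression to the mean from selecting on MFR <3.0 with the same scan, time trends and differences in acquisition between visits all remain. The change is worth making because it is cheap, but its absence does not invalidate the trial.

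**What to change.** Amend section 7.3.1, with a cross-reference in 6.10:

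1. Use the screening quantification for eligibility only.
2. After the last week-12 scan, remove date and visit labels from the stored baseline and week-12 PET data of every patient and put them in random order.
3. Have the staff who already do the quantification process them in one batch. State how the blood-pool region is placed and by whom.
4. Use these values for the primary MFR analysis and the secondary rest and stress MBF analyses, and adapt the baseline definition in 8.5.2 accordingly.

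**Cost.** 11–20 baseline scans are processed a second time, and the week-12 endpoint values wait until the last patient has finished. The dynamic data must be kept; section 10.2 names PET images but does not expressly name the list-mode data, so this should be written in. No new scan, patient or reader is needed, and the 11 evaluable patients are unchanged. The report should still name regression to the mean and time trends as limits of the design.

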7.3.2 Echocardiography

Ejection fraction (EF%), left ventricular end systolic diameter (LVESD), interventricular septum thickness (IVST), left ventricular posterior wall thickness (PWT) and E/A ratio

7.3.3 Seattle angina questionnaire

1. The Seattle Angina Questionnaire is designed to quantify the physical and emotional effects of coronary artery disease. This instrument (Appendix II) is a 19-item self-administered questionnaire resulting in five scales that measure clinically important dimensions of coronary artery disease: physical limitation, anginal stability, anginal frequency, treatment satisfaction and disease perception;
2. The Seattle Angina Questionnaire is scored by assigning each response an ordinal value, beginning with 1 for the response that implies the lowest level of functioning, and summing across items within each of the five scales. Scale scores are then transformed to a 0 to 100 range by subtracting the lowest possible scale score, dividing by the range of the scale and multiplying by 100. Because each scale monitors a unique dimension of coronary artery disease, no summary score is generated.
3. The Seattle Angina Questionnaire could be finished by a single page of paper. The answers will be copied in the eCRF by investigators as soon as it is completed. It is designed to be self-administered. For patients who can't read, investigators or other family persons could read the questions for them, then the patients could choose the most appropriate answers which the questioners tick them in the paper for the patients. For those who could read, they should complete it by themselves

7.4 Assessment of Safety

The safety profile of IMP will be assessed through the recording, reporting and analyzing of baseline medical conditions, adverse events, physical examination findings including vital signs and laboratory tests.

Comprehensive assessment of any apparent toxicity experienced by the subject will be performed throughout the course of the trial, from the time of the subject's signature of informed consent. Trial site personnel will report any adverse event (AE), whether observed by the Investigator or reported by the subject (see Section 7.4.1.2, "Methods of Recording and Assessing Adverse Events").

The reporting period for adverse events is described in Section 7.4.1.3.

7.4.1 Adverse Events

7.4.1.1 Adverse Event Definitions

Adverse Event

An adverse event (AE) is any untoward medical occurrence in a subject or clinical investigation subject administered a pharmaceutical product, which does not necessarily have a causal relationship with this treatment. An AE can therefore be any unfavorable and unintended sign (including an abnormal laboratory finding), symptom, or disease temporally associated with the use of a medicinal product, whether or not considered related to the medicinal product.

In cases of surgical or diagnostic procedures, the condition/illness leading to such a procedure is considered as the AE rather than the procedure itself.

In case of a fatality, the cause of death is considered as the AE, and the death is considered as its OUTCOME.

Adverse Reaction(ADR)

In accordance with GCP, adverse drug reaction is an adverse event considered related to drug treatment.

Serious Adverse Event

A serious adverse event (SAE) is any untoward medical occurrence that at any dose:

Results in death.

Is life-threatening.

NOTE: The term “life-threatening” in this definition refers to an event in which the subject is at risk of death at the time of the event; it does not refer to an event that hypothetically might cause death if it were more severe.

Requires inpatient hospitalization or prolongation of existing hospitalization.

Results in persistent or significant disability/incapacity.

Is a congenital anomaly/birth defect.

Is otherwise considered as medically important.

Important medical events that may not result in death, be life-threatening, or require hospitalization may be considered as SAEs when, based upon appropriate medical judgment, they may jeopardize the subject or may require medical or surgical intervention to prevent one of the outcomes listed in this definition. Examples of such events include allergic bronchospasm requiring intensive treatment in an emergency room or at home, blood

dyscrasias or convulsions that do not result in inpatient hospitalization, or the development of drug dependency or drug abuse.

For the purposes of reporting, any suspected transmission of an infectious agent via the IMP is also considered a serious adverse reaction and all such cases should be reported in an expedited manner as described in Section 7.4.1.4.

Events that Do Not Meet the Definition of an SAE

Elective hospitalizations to administer, or to simplify trial treatment or trial procedures (e.g. an overnight stay to facilitate chemotherapy and related hydration therapy application) are not considered as SAEs. However, all events leading to unplanned hospitalizations or unplanned prolongation of an elective hospitalization (e.g., undesirable effects of any administered treatment) must be documented and reported as SAEs.

Events Not to Be Considered as AEs/SAEs

Medical conditions present at the initial trial visit that do not worsen in severity or frequency during the trial are defined as Baseline Medical Conditions, and are NOT to be considered AEs.

Severity of AEs

The Investigator is required to grade the severity of each adverse event.

Investigators will reference the National Cancer Institute - Common Terminology Criteria for Adverse Events (CTCAE), version 4.0 (publication date: 28 May 2009). This is a descriptive terminology that can be used for adverse event reporting.

A general grading (severity/intensity) scale is provided at the beginning of the referenced document, and specific event grades are also provided.

If a particular AE's severity/intensity is not specifically graded by the guidance document, the Investigator is to revert to the general definitions of Grade 1 through Grade 5 and use his or her best medical judgment.

The 5 general grades are:

Grade 1: Mild

Grade 2: Moderate

Grade 3: Severe

Grade 4: Life-threatening or disabling

Grade 5: Death related to AE*

According to the Sponsor's convention, if a severity/intensity of Grade 4 or 5 is applied to an AE, then the Investigator must also report the event as a serious adverse event (SAE; see definition below) as per Section 7.4.1.4. However, a laboratory abnormality with a

severity/intensity of Grade 4, such as anemia or neutropenia, is considered serious only if the condition meets one of the serious criteria described above.

*Note: Death (Grade 5 as defined by NCI-CTCAE version 4.0) is mainly regarded as an outcome, to be documented as described below.

In the case of death, the primary cause of death (the event leading to death) should be recorded and reported as an SAE. “Fatal” will be recorded as the outcome of this respective event; death will not be recorded as separate event. Only if no cause of death can be reported (e.g., sudden death, unexplained death), the death per se might be reported as an SAE.

Causal relationship of AEs to the IMP

Investigators must also systematically assess the causal relationship of AEs to the IMP using the following definitions.

Not related: Not suspected to be related to the IMP. AE could not medically (pharmacologically/clinically) be attributed to the IMP under study in this clinical trial protocol. A reasonable alternative explanation must be available.

Related: Suspected to be related to the IMP. AE could medically (pharmacologically/clinically) be attributed to the IMP under study in this clinical trial protocol.

Abnormal Laboratory Findings and Other Abnormal Investigational Findings

Abnormal laboratory findings and other abnormal investigational findings (e.g. on an ECG trace) should not be reported as AEs unless they are associated with clinical signs and symptoms, lead to treatment discontinuation or are considered otherwise medically important by the Investigator. If an abnormality fulfills these criteria, the identified medical condition (e.g. anemia, increased ALT) must be reported as the AE rather than the abnormal value itself.

